8.1.3.3. US FDA Harmonized Case Definition for COVID-19

If a participant presents with symptoms as those listed by the US FDA harmonized case definition¹⁴ (see [Appendix 10](#)), the investigator (or designated medically trained clinician) should assess if these are suggestive of COVID-19:

- A SARS-CoV-2 positive RT-PCR or molecular test result from any available respiratory tract sample (eg, nasal swab sample, sputum sample, throat swab sample, saliva sample) or other sample; **AND**

^a Participants will be asked to undertake the COVID-19 procedures until 14 days after symptom onset (COVID-19 Day 15) or until **resolution of the COVID-19 episode**, whichever comes last (see Section 8.1.2).

- COVID-19 symptoms consistent with those defined by the US FDA harmonized case definition¹⁴ at the time of finalization of this protocol: fever or chills, cough, shortness of breath or difficulty breathing, fatigue, muscle or body aches, headache, new loss of taste or smell, sore throat, congestion or runny nose, nausea or vomiting, diarrhea.

8.1.3.4. Case Definition for Asymptomatic or Undetected COVID-19

If a participant does not fulfil the criteria for suspected COVID-19 based on signs and symptoms (see Section 8.1.1), which would classify them as mild or moderate to severe/critical by the protocol definitions mentioned above (Section 8.1.3.1 and Section 8.1.3.2).

AND

- has a SARS-CoV-2 positive RT-PCR or molecular test result from any available respiratory tract sample (eg, nasal swab sample, sputum sample, throat swab sample, saliva sample) or other sample

OR

- develops a positive serology (non-S protein) test

Then, the participant will be considered to have experienced asymptomatic or undetected COVID-19.

A molecularly confirmed positive RT-PCR for SARS-CoV-2 will need to be captured in the eCRF.

As of Amendment 7, severity assessment by the CSAC may still be performed and will be based on the data collected through the passive follow-up (eg, hospitalization reported in the context of SAEs). The scope of the severity review may change and will be described in the charter.

8.1.3.5. SARS-CoV-2 Seroconversion Assessment

For samples collected prior to implementation of Amendment 7, an immunologic test for SARS-CoV-2 seroconversion (ELISA and/or SARS-CoV-2 immunoglobulin assay) based on SARS-CoV-2 N protein, may be performed to identify cases of asymptomatic infection on samples obtained at Day 1 (before the 1st vaccination) and 14 days, 6 months, and 1 year after the second vaccination (see Section 8.1.4) and at the unblinding visit and at the Booster Vaccination Visit.

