All enrolled participants will have a blood sample taken at the time of the unblinding visit (before open-label vaccination) and at the Booster Vaccination Visit (before booster vaccination) for analysis of immune responses, regardless of whether they were part of the Immunogenicity Subset in the double-blind phase.

Up to Amendment 7, during a COVID-19 episode, blood will be collected on COVID-19 Day 3-5 and on COVID-19 Day 29 for immunogenicity assessments, including the assays summarized in **Table 5**. As from Amendment 7, active follow-up will no longer be pursued and blood sampling for this purpose will no longer be performed.

Table 5: Immunogenicity Assays

Humoral Assays	Purpose
Supportive of Secondary Objectives	
SARS-CoV-2 binding antibodies to S protein (ELISA)	Analysis of antibodies binding to SARS-CoV-2 S protein
SARS-CoV-2 seroconversion based on antibodies to N protein (ELISA and/or SARS-CoV-2 immunoglobulin assay)	Analysis of antibodies binding to SARS-CoV-2 N protein
Supportive of Exploratory Objectives	
SARS-CoV-2 neutralization (VNA)	Analysis of neutralizing antibodies to the wild-type or variant virus, and/or pseudovirion expressing S protein
SARS-CoV-2 binding antibodies to S protein (MSD)	Analysis of antibodies binding to SARS-CoV-2 S protein (different than the assays supportive of the secondary objectives) and the receptor-binding domain (RBD) of SARS-CoV-2 S protein
Functional and molecular antibody characterization	Analysis of antibody characteristics including, but not limited to, avidity, Fc-mediated viral clearance, Fc characteristics, Ig subclass, IgG isotype, antibody glycosylation, and assessment of antibody repertoire
Adenovirus neutralization (VNA)	Adenovirus neutralization assay to evaluate neutralizing antibody responses against the Ad26 vector
Binding antibodies to other coronaviruses (MSD)	Analysis of antibodies binding to coronaviruses other than SARS-CoV-2

Ad26 adenovirus type 26; ELISA enzyme linked immunosorbent assay; Fc crystallizable fragment; Ig(G) immunoglobulin (G); MSD Meso Scale Discovery; N nucleocapsid; RBD receptor binding domain; S spike; SARS CoV 2 severe acute respiratory syndrome coronavirus 2; VNA virus neutralization assay.

In areas where seroprevalence is predicted to be high, a screening serologic test for past or current infection with SARS-CoV-2 may be performed (in a local laboratory) at the discretion of the sponsor to restrict the proportion of seropositive participants in the study.

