9.2. Sample Size Determination

9.2.1. Efficacy (Total Sample Size)

For the double-blind phase, the sample size is determined using the following assumptions:

- a VE for molecularly confirmed, moderate to severe/critical SARS-CoV-2 infection of 65%.
- type 1 error rate $\alpha = 2.5\%$ to evaluate VE of the vaccine regimen.
- a randomization ratio of 1:1 for active versus placebo

Events are defined as first occurrence of molecularly confirmed, moderate to severe/critical COVID-19 according to the case definition in Section 8.1.3.1 in the PP population at least 14 days after the second vaccination with study vaccine (Day 71).

Under the assumptions above, a total of 104 events will provide approximately 90% power to reject the null hypothesis of $H_0: VE \leq 30\%$, according to the primary endpoint case definition of moderate to severe/critical COVID-19 (Section 8.1.3.1).

If the primary hypothesis testing is successful, secondary objectives will be evaluated against a null hypothesis employing a lower limit $VE > 0\%$. The method to perform hypothesis testing of primary and secondary objectives preserving the FWER will be specified in the SAP. The FWER will be controlled at 2.5%.

Sample Size Justification

Based on the variations in seroprevalence, degree of social distancing and use of personal protective equipment, it is not feasible to estimate the incidence rates that can be attained at the time of the start of this study. It is also unknown which local regulations (eg, potential lockdowns) will be in effect at that time.

The sample size is approximately 15,000/group (approximately 30,000 in total) and is determined based on estimated annualized incidence rate of moderate to severe/critical COVID-19 of 1% to 4% at the start of the study.

Assuming 2 months of recruitment and 10% seroprevalence, the selected sample size will have a high probability (approximately 90%) to have reached an efficacy signal within 15 months after first participant vaccinated for an assumed $VE \geq 65\%$ under an assumed incidence of 1.4% in Month 1-3, and waning of incidence thereafter, eg, 50% reduction at Month 4 (0.70% annualized) followed by further reduction to 0.58%.

With higher incidences at the start of the study, the timelines to efficacy will shorten.

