9.4.1. Primary Endpoint Evaluation for the Double-blind Phase

The double-blind phase of the study is designed to test the primary hypothesis of VE in the PP population: H0: VE $\leq 30\%$ versus H1: VE $> 30\%$ and will be evaluated at a 2.5% 1-sided significance level.

The primary endpoint will evaluate the first occurrence of molecularly confirmed, moderate to severe/critical COVID-19 according to the case definition in Section 8.1.3.1, with onset at least 14 days after the second vaccination (Day 71) with Ad26.COV2.S versus placebo, in the PP population, including all events from both age groups, with and without comorbidities.

Participants included in the seronegative analysis set are those participants with a negative SARS-CoV-2 serology test result at baseline.

The unblinding visit marks for a participant the end of the double-blind phase, and the start of the open-label phase. For a given participant, all data up to the unblinding visit will be incorporated in the analysis of the double-blind phase.

The minimum criteria that may trigger the primary analysis before at least 90% of participants are unblinded is if the prespecified harm boundaries have been crossed.

A successful primary efficacy conclusion will require establishing the hypothesis H1: VE $> 30\%$ for the primary endpoint.

Exact Poisson regression will be used to estimate the VE and associated CI taking into account the follow-up time. To evaluate the primary null hypothesis: H0: VE $\leq 30\%$ versus H1: VE $> 30\%$ for the primary endpoint, 95% 2-sided confidence interval based on Poisson regression model will be used.

The decision rules for harm are detailed in Section 9.4.1.1.

For any case definition to be considered for classification of COVID-19 cases, there needs to be at least one SARS-CoV-2 positive RT-PCR or molecular test result from any available respiratory tract sample (eg, nasal swab sample, sputum sample, throat swab sample, saliva sample) that is confirmed by the central laboratory. It is possible that not all samples can be confirmed at the time of the analysis. Hence, a sensitivity analysis may be performed using all RT-PCR or molecular test result, regardless of the confirmation by the central laboratory.

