At the time of the primary analysis VE against any infection will be evaluated. At the time of the primary analysis, available N-ELISA measurements will be incorporated to evaluate VE against any infection, including asymptomatic infection. A participant will be defined as having any infection whether he/she had either a symptomatic infection (mild, moderate or severe according to the case definition) or an asymptomatic infection (as defined in Section 8.1.3.4). When all participants had 6 months of follow-up, the available N-ELISA measurements will be used to evaluate VE against asymptomatic/undetected infections only. Poisson regression will be used to estimate the VE and associated 95% confidence interval in seronegative participants in the PP analysis set for each of both analyses.

Among participants with SARS-CoV-2 infection, the effect of the study vaccine on the viral load levels at and after diagnosis as well as on the duration of SARS-CoV-2 viral load positivity will be evaluated.

The effect of the vaccine will be evaluated against molecularly confirmed COVID-19 infections requiring medical intervention once sufficient events are available. Medical interventions are evaluated as a composite endpoint of hospitalization, ICU admission, mechanical ventilation and ECMO, linked to objective measures such as decreased oxygenation, X-ray or CT findings. Poisson regression will be used to estimate the VE and the associated 95% confidence interval in seronegative participants in the PP analysis set.

All VE evaluations will be repeated regardless of their serostatus.

The statistical analysis for secondary endpoints, multiple testing strategy to evaluate the secondary objectives and the timing of the hypothesis testing will be detailed in the SAP.

See also Section 9.4.1.

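### VE against any infection counts N-seroconversions as infections and so assumes, unstated and unchecked, that infected vaccinees seroconvert to N as often as infected placebo recipients

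*Protocol*

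**What the plan says.** Protocol Section 8.1.3.4 defines an asymptomatic or undetected case as a participant without qualifying symptoms who either has a positive molecular test or "develops a positive serology (non-S protein) test". The serology route is sufficient alone and is the same in both arms.

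Section 8.1.3.5 names the assay, "based on SARS-CoV-2 N protein, may be performed to identify cases of asymptomatic infection". The visits are Day 1, then 14 days, 6 months and 1 year after the second vaccination, plus the unblinding and booster visits.

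Section 9.4.2 says that at the primary analysis "available N-ELISA measurements will be incorporated to evaluate VE against any infection, including asymptomatic infection". Once all participants have 6 months of follow-up, the same measurements serve for VE against asymptomatic or undetected infection only. Both use Poisson regression in seronegative per-protocol participants. The next paragraph of that section plans to evaluate, among infected participants, "the effect of the study vaccine on the viral load levels at and after diagnosis" and the duration of positivity.

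Section 8.1.3 makes asymptomatic infection a secondary objective. Section 9.2.1 evaluates secondary objectives against VE of 0% and adds "The FWER will be controlled at 2.5"%.

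On sampling, Section 8.1.4 says that during an episode, up to Amendment 7, "blood will be collected on COVID-19 Day 3-5 and on COVID-19 Day 29 for immunogenicity assessments", with the assays of Table 5. Table 5 includes the N assay.

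**The concern.** N antibody is the host's response to viral antigen, not a direct record of infection. A ratio of N-seroconversion rates equals a ratio of infection rates only if the chance of seroconverting once infected is the same in both arms. The protocol itself gives a reason to ask. If the vaccine lowers viral load or shortens positivity, infected vaccinees see less antigen and may seroconvert to N less often. Infections would then be missed more in the vaccine arm, and the missing cases would be read as prevented.

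Serology matters here because, in the text reviewed, a symptom-free participant has no scheduled swab between baseline and the unblinding visit unless a positive outside RT-PCR is reported. The only assay interference discussed is spike-assay false positives after vaccination (footnote to Section 8.2.2). That supports the choice of N but does not address N-seroconversions missed by arm.

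At stake is the meaning of a secondary result: prevention of infection, or prevention of N-seroconversion.

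**Working it through.** **The plan's own figure.** Section 9.2.1 assumes "a VE for molecularly confirmed, moderate to severe/critical SARS-CoV-2 infection of 65"%, 1:1 allocation and 104 events for about 90% power against VE ≤ 30%. The test "will be evaluated at a 2.5% 1-sided significance level". By an exact conditional binomial test, the vaccine-arm share of events is 0.70/1.70 under the null and 0.35/1.35 under the alternative. Rejecting at 32 or fewer of 104 gives an exact level of 1.9% and power of 89.1%. The figure reproduces. It concerns a molecularly confirmed endpoint and is not affected by this point.

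**Notation.** None of these values is given in the documents for this purpose.
- q: share of placebo infections that are symptomatic. These are taken to be molecularly confirmed in both arms.
- c: share of those infections that the vaccine turns asymptomatic.
- s: chance that an asymptomatic placebo infection is detected by N serology.
- r: N-seroconversion probability in infected vaccinees divided by that in infected placebo recipients.

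**Any infection.** Detected cases per infection:
- placebo: q + (1 − q)s
- vaccine: q(1 − c) + [1 − q(1 − c)]·s·r

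Apparent VE = 1 − (1 − true VE) × (vaccine ÷ placebo).

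Take true VE = 0, q = 0.4, c = 0.65 and s = 1. The 65% is borrowed from the primary-endpoint assumption for illustration. Placebo = 1. Vaccine = 0.14 + 0.86r.
- r = 1: 1.000, apparent VE 0%
- r = 0.8: 0.14 + 0.688 = 0.828, apparent VE 17%
- r = 0.6: 0.14 + 0.516 = 0.656, apparent VE 34%

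Chance that the exact one-sided 2.5% test of VE ≤ 0 rejects, by assumed number of detected events:

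| r | 104 | 200 | 400 |
|---|---|---|---|
| 1.0 | 2% | 2% | 2% |
| 0.8 | 13% | 24% | 43% |
| 0.6 | 53% | 82% | 98% |

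Sensitivity to the other inputs: with q = 0.6, apparent VE is 16% (r = 0.8) and 32% (r = 0.6). With q = 0.4 and s = 0.9, it is 19% and 36%, and 3% even at r = 1, because converted cases move to a less sensitive route.

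**Asymptomatic infection only.** The same shift raises the vaccine-arm count. Under the same inputs, asymptomatic infections per 100 infected are 86 (vaccine) against 60 (placebo), a ratio of 0.86/0.60 = 1.43. Apparent VE = 1 − 1.43r:
- r = 0.9: −29%
- r = 0.8: −15%
- r = 0.7: 0%
- r = 0.6: 14%
- r = 0.5: 28%

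The two effects cancel near r = 0.60/0.86 = 0.70.

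**The limiting case.** Apparent VE = 1 − (1 − VE)r holds only if every case is found by N serology and the vaccine shifts no cases from symptomatic to asymptomatic. With true VE of 0 and r = 0.8 it gives 20%, and rejection rates of 18%, 32% and 57% at 104, 200 and 400 events. If half of the placebo cases are found by RT-PCR equally in both arms, the ratio is 0.5 + 0.5 × 0.8 = 0.9, and the rates fall to 6%, 10% and 16%.

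**The case against.** The strongest reply is that the premise is not established. Section 9.4.2 says the viral-load effect will be evaluated, not that there is one, and no section links viral load to N-seroconversion. Every r above is assumed, and at r = 1 with full detection nothing goes wrong. This stands: the point is conditional.

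Second, a molecular test also makes a case, and symptomatic cases are molecularly confirmed, so the bias is diluted. This stands as well, although the share found by PCR among symptom-free participants is unknown.

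Third, Section 9.4.2 leaves the detail of secondary analyses to the SAP, which was not at hand and may contain a sensitivity analysis. This limits the point to what the protocol fixes: the case definition and the use of its counts as VE against infection.

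A reader might infer that VE is inflated by exactly the factor r, or that a vaccine with no effect on infection would be declared protective against asymptomatic infection. The documents support neither. The first ignores the molecular route; the second ignores the shift from symptomatic to asymptomatic disease, which can cancel or reverse the bias.

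**Conclusion.** This is a cheap improvement, not a demonstrated error. The protocol fixes N-seroconversion as sufficient evidence of infection in either arm and turns the counts into VE, which needs equal detectability by arm. The text reviewed does not state or check that condition. If r is below 1, VE against any infection is biased upward: 17% at r = 0.8 and 34% at r = 0.6 when no infection is prevented, under assumed q = 0.4, c = 0.65 and s = 1. For asymptomatic-only VE the net direction is uncertain. The primary endpoint's case definition is molecular and stands apart from this.

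It would go too far to say that the 2.5% error rate is known to be lost. That depends on r, on the PCR share and on the testing order, which the protocol leaves to the SAP.

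**What to change.** Add to Section 9.4.2:

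1. Among PCR-confirmed participants with a COVID-19 Day 29 sample, report the proportion who seroconvert to N by arm with a confidence interval, by severity or viral load where numbers allow. Under Section 8.1.2.2 these are participants positive on the Day 1-2 or Day 3-5 swab. A positive unblinding-visit swab does not by itself lead to a Day 29 draw.
2. Prespecify a tipping-point analysis of VE against any infection and against asymptomatic infection over a stated range of r, applied only to serology-detected cases. Interpret the serology-based result as VE against N-seroconversion unless it is robust over a plausible range of r.

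The cost is wording and one extra analysis on samples already planned, with a wider or less favourable range for these secondary endpoints. Because r would be estimated mainly in symptomatic cases, it should inform the range, not act as a direct correction or a formal gate for a claim. A PCR-only VE from the single unblinding swab is not a clean reference either, since it also depends on viral load and duration of positivity.

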8.1.3.6. Clinical Severity Adjudication Committee

The Clinical Severity Adjudication Committee will be utilized for adjudication of the severity of COVID-19 cases taking into account all available relevant information at the time of adjudication. As of Amendment 7, Clinical Severity Adjudication Committee may review all cases based on available data from the passive follow-up (eg, limited to COVID-19 AE/SAE data, CIOMS forms, local laboratory results). The Clinical Severity Adjudication Committee's decisions will be considered the definitive classification of the case. The role of the Committee and adjudication process will be provided in the committee's charter and more details regarding the impact on the analysis will be provided in the SAP. The case review including severity assessments after implementation of Amendment 7 may change and will be reflected in the charter of the committee.

8.1.4. Immunogenicity Assessments

Up to Protocol Amendment 7, blood will be collected from all non-Immunogenicity Subset participants for humoral immunogenicity assessments at Day 1 (before the 1st vaccination), 14 days, 6 months and 1 year after the second vaccination.

In the double-blind phase, for a total of approximately 400 participants in the Immunogenicity Subset, blood will be collected for analysis of humoral immune responses before each vaccination, 28 days after the 1st vaccination and 14 days, 6 months, 1 year, 18 months, and 2 years after the second vaccination.

For a total of approximately 400 participants in the new Immunogenicity Subset, blood will be collected for analysis of humoral immune responses at baseline and at Day 71, Week 32, and Week 60 after the first vaccination.

All participants in the Immunogenicity Subset will be enrolled from Study Stage 2. Participants in the Immunogenicity Subset in the double-blind phase and in the open-label phase (referred to as Subset "B") will be divided into 4 groups as presented in [Table 3](#) and [Table 4](#), respectively.

Table 3: Sample Size and Distribution of the Immunogenicity Subset Between Active and Placebo Groups

Study Vaccine	Subset 1a	Subset 1b	Subset 2a	Subset 2b
5×10 ¹⁰ vp/5×10 ¹⁰ vp	50	50	50	50
Placebo/placebo	50	50	50	50
Total	100	100	100	100

vp virus particles

Subset 1a: healthy participants ≥18 years to <60 years of age without relevant comorbidities, enrolled during Stage 2.

Subset 1b: healthy participants ≥60 years of age without relevant comorbidities, enrolled during Stage 2.

Subset 2a: participants ≥18 to <60 years of age with relevant comorbidities, enrolled during Stage 2.

Subset 2b: participants ≥60 years of age with relevant comorbidities, enrolled during Stage 2

Table 4: Sample Size and Distribution of the Immunogenicity Subset B for the Open-label Phase

Study Vaccine	Subset B1a	Subset B1b	Subset B2a	Subset B2b
5×10 ¹⁰ vp, 5×10 ¹⁰ vp	50	50	50	50
5×10 ¹⁰ vp	50	50	50	50
Total	100	100	100	100

vp virus particles

Subset B1a: healthy participants ≥18 years to <60 years of age without relevant comorbidities.

Subset B1b: healthy participants ≥60 years of age without relevant comorbidities.

Subset B2a: participants ≥18 to <60 years of age with relevant comorbidities.

Subset B2b: participants ≥60 years of age with relevant comorbidities.

All enrolled participants will have a blood sample taken at the time of the unblinding visit (before open-label vaccination) and at the Booster Vaccination Visit (before booster vaccination) for analysis of immune responses, regardless of whether they were part of the Immunogenicity Subset in the double-blind phase.

Up to Amendment 7, during a COVID-19 episode, blood will be collected on COVID-19 Day 3-5 and on COVID-19 Day 29 for immunogenicity assessments, including the assays summarized in **Table 5**. As from Amendment 7, active follow-up will no longer be pursued and blood sampling for this purpose will no longer be performed.

Table 5: Immunogenicity Assays

Humoral Assays	Purpose
Supportive of Secondary Objectives	
SARS-CoV-2 binding antibodies to S protein (ELISA)	Analysis of antibodies binding to SARS-CoV-2 S protein
SARS-CoV-2 seroconversion based on antibodies to N protein (ELISA and/or SARS-CoV-2 immunoglobulin assay)	Analysis of antibodies binding to SARS-CoV-2 N protein
Supportive of Exploratory Objectives	
SARS-CoV-2 neutralization (VNA)	Analysis of neutralizing antibodies to the wild-type or variant virus, and/or pseudovirion expressing S protein
SARS-CoV-2 binding antibodies to S protein (MSD)	Analysis of antibodies binding to SARS-CoV-2 S protein (different than the assays supportive of the secondary objectives) and the receptor-binding domain (RBD) of SARS-CoV-2 S protein
Functional and molecular antibody characterization	Analysis of antibody characteristics including, but not limited to, avidity, Fc-mediated viral clearance, Fc characteristics, Ig subclass, IgG isotype, antibody glycosylation, and assessment of antibody repertoire
Adenovirus neutralization (VNA)	Adenovirus neutralization assay to evaluate neutralizing antibody responses against the Ad26 vector
Binding antibodies to other coronaviruses (MSD)	Analysis of antibodies binding to coronaviruses other than SARS-CoV-2

Ad26 adenovirus type 26; ELISA enzyme linked immunosorbent assay; Fc crystallizable fragment; Ig(G) immunoglobulin (G); MSD Meso Scale Discovery; N nucleocapsid; RBD receptor binding domain; S spike; SARS CoV 2 severe acute respiratory syndrome coronavirus 2; VNA virus neutralization assay.

In areas where seroprevalence is predicted to be high, a screening serologic test for past or current infection with SARS-CoV-2 may be performed (in a local laboratory) at the discretion of the sponsor to restrict the proportion of seropositive participants in the study.

For samples collected prior to implementation of Amendment 7, a serologic test for past or current infection with SARS-CoV-2 may be performed for all participants at Day 1 (before the 1st vaccination) and 14 days and 6 months after the second vaccination. All participants in the open-label phase will have 1 blood sample taken at the unblinding visit (before open-label vaccination) and at the Booster Vaccination Visit (before booster vaccination), except when the previous blood sampling for the serologic test occurred within 5 days of the visit.^a Samples for the

^a The unblinding visit and the Booster Vaccination Visit may be combined with the scheduled study visit and procedures that would be duplicated should be done only once. If a blood draw is planned in the scheduled visit no additional blood draw is needed.

serologic tests will be sent to a central laboratory for testing.^a Participants who test positive will be informed of the result by the study staff.

